## **6.1 Adverse Event Reporting Period**

For the current study, the adverse event reporting period is the 6 month study duration. Participants will also be encouraged to contact the study team to report any additional adverse events during the 6 months following study completion.

## **6.2 Preexisting Condition**

A preexisting condition is one that is present at the start of the study. A preexisting condition should be recorded as an adverse event if the frequency, intensity, or the character of the condition worsens during the study period.

At screening, any clinically significant abnormality should be recorded as a preexisting condition. At the end of the study, any new clinically significant findings/abnormalities that meet the definition of an adverse event must also be recorded and documented as an adverse event.

## **6.3 Post-study Adverse Event**

All unresolved AEs will be followed by the study team until the events are resolved, the subject is lost to follow-up, or the AE is otherwise explained. A review of AEs which the subject or subject's physician believe might reasonably be related to participation in the study will be performed up to 6 months following study completion.

## **6.4 Hospitalization, Prolonged Hospitalization or Surgery**

Any AE related to the study intervention that results in hospitalization or surgery should be documented and reported as a serious AE.

Neither the condition, hospitalization, prolonged hospitalization, nor surgery are reported as an adverse event in the following circumstances:

- Hospitalization or prolonged hospitalization for diagnostic or elective surgical procedures for a preexisting condition. Surgery should not be reported as an outcome of an adverse event if the purpose of the surgery was elective or diagnostic and the outcome was uneventful.

## **6.5 Recording of Adverse Events**

The study team will seek information on adverse events by specific questioning between baseline and the follow-up visits. Information on all adverse events will be recorded immediately in the adverse event section of the specific questionnaire as well as in an adverse event form (see Attachment – Adverse Event Form).

All adverse events occurring during the study period will be recorded. The clinical course will be followed until resolution, stabilization, or until it has been ultimately determined that the study treatment or participation is not the probable cause. Serious adverse events that are still ongoing at the end of the study period will be followed up, to determine the final outcome. Any serious adverse event that occurs after the study period and is considered to be at least possibly related to the study treatment or study participation will be recorded and reported immediately.

## **6.6 Reporting of Serious Adverse Events and Unanticipated Problems**

When an adverse event has been identified, the study team will take appropriated action necessary to protect the study participant and then complete the Adverse Event Form. The sponsor-investigator will evaluate the event and determine the necessary follow-up and reporting required.

### **6.6.1 Sponsor-investigator Reporting: Notifying the Mayo IRB**

An adverse event form will be completed for any serious adverse event. This will be reported to the Mayo IRB in a de-identified manner.

The study team will report to the Mayo IRB any UPIRTSOs and NonUPIRTSOs according to the Mayo IRB Policy and Procedures.

Information collected on the adverse event form (and entered into the research database)

- Subject's ID
- Description of adverse event
- The date the adverse event occurred and resolved (if applicable)
- Intensity
- Outcome

- Action taken to address
- Relationship to study
- Impact on study withdrawal
- Classification as serious or not

The sponsor-investigator will review all adverse event reports to determine if specific reports need to be made to the IRB. The sponsor-investigator will sign and date the adverse event report when it is reviewed. For this protocol, only directly related SAEs/UPIRTSOs will be reported to the IRB.

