## 6 Safety and Adverse Events

### Definition of Adverse Event

Unanticipated Problems Involving Risk to Subjects or Others (UPIRTSO) - any unanticipated problem or adverse event that meets the following three criteria:

Serious: Serious problems or events that results in significant harm, (which may be physical, psychological, financial, social, economic, or legal) or increased risk for the subject or others (including individuals who are not research subjects). These include: (1) death; (2) life threatening adverse experience; (3) hospitalization - inpatient, new, or prolonged; (4) disability/incapacity - persistent or significant; (5) breach of confidentiality and (6) other problems, events, or new information (i.e. publications, interim findings, product labeling change) that in the opinion of the local investigator may adversely affect the rights, safety, or welfare of the subjects or others, or substantially compromise the research data, AND

Unanticipated: (i.e. unexpected) problems or events are those that are not already described as potential risks in the protocol, consent document, not listed in the Investigator's Brochure, or not part of an underlying disease. A problem or event is "unanticipated" when it was unforeseeable at the time of its occurrence. A problem or event is "unanticipated" when it occurs at an increased frequency or at an increased severity than expected, AND

Related: A problem or event is "related" if it is possibly related to the research procedures.

Adverse Event - an untoward or undesirable experience associated with the use of a medical product (i.e. drug, device, biologic) in a patient or research subject.

Serious Adverse Event - adverse events are classified as serious or non-serious. Serious problems/events can be well defined and include:

- Death
- Life threatening adverse experience
- Hospitalization
- Inpatient, new, or prolonged; disability/incapacity
- And/or per protocol may be problems/events that in the opinion of the sponsor-investigator may have adversely affected the rights, safety, or welfare of the subjects or others, or substantially compromised the research data.

All AEs that do not meet any of the criteria for serious, should be regarded as non-serious AEs.

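### Section 6.6.1 ends by limiting IRB reports to 'directly related' events, an undefined bar stricter than the protocol's own 'possibly related' test

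*Combined protocol and SAP*

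**What the plan says.** Section 6.6.1 contains three statements on what goes to the IRB.

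- On SAEs: "An adverse event form will be completed for any serious adverse event. This will be reported to the Mayo IRB in a de-identified manner". No relatedness condition is attached.
- On unanticipated problems: "The study team will report to the Mayo IRB any UPIRTSOs and NonUPIRTSOs according to the Mayo IRB Policy and Procedures".
- At the end of the section: "For this protocol, only directly related SAEs/UPIRTSOs will be reported to the IRB".

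Just before the last of these, the protocol gives the decision to one role: "The sponsor-investigator will review all adverse event reports to determine if specific reports need to be made to the IRB". Section 6.6 says much the same: "The sponsor-investigator will evaluate the event and determine the necessary follow-up and reporting required".

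The definitions at the start of section 6 make an event a UPIRTSO when it is serious, unanticipated and related. For the third element, an event counts as related "if it is possibly related to the research procedures". Section 6.5 uses 'at least possibly related' for SAEs that arise after the study period and asks for immediate reporting, without naming the recipient. Section 6.6.2 uses a further wording, 'reasonably' related to the device, for stopping therapy. It halts the study for IRB re-review once 5 patients have SAEs.

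**The concern.** The closing sentence of 6.6.1 sets a narrower reporting rule than the sentences before it, and does so with a term found nowhere else in the document. A coordinator holding a serious event judged possibly but not directly related is told to send it by the opening of the section and not to send it by the end.

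What is at stake is safety oversight while the study is running. Section 6.6.3 gives medical monitoring to the study investigator, and section 6 names no independent monitor or safety board. The IRB is the only outside recipient of safety reports that section 6 names. If the closing sentence is followed, whether a possibly related serious event reaches the IRB rests on one role's reading of an undefined word.

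**Working it through.** The documents state no figure on this point and no arithmetic is needed. The check sets the rules side by side and asks what each does with four kinds of event.

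**Inputs.** The opening SAE rule, the UPIRTSO rule and the closing sentence come from 6.6.1. The relatedness test comes from the section 6 definitions. The wording for later events comes from 6.5.

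| Event during the study | Opening SAE rule | UPIRTSO rule | Closing sentence |
|---|---|---|---|
| SAE, directly related | report | as policy directs | report |
| SAE, unanticipated, possibly but not directly related (a UPIRTSO by section 6) | report | report, as policy directs | do not report |
| SAE, anticipated, possibly but not directly related (not a UPIRTSO) | report | as policy directs | do not report |
| SAE, unrelated | report | as policy directs | do not report |

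**Step 1: is 'directly related' defined?** No. The term occurs only in the closing sentence of 6.6.1. The adverse event form records the relationship to the study, but the protocol gives no scale for it.

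**Step 2: is it stricter than the section 6 test?** With no scale, only plain meaning is available. 'Directly' asks for more than 'possibly'. An event can therefore satisfy section 6 and fail the closing sentence.

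**Step 3: does the conflict survive a narrowing reading?** Suppose the closing sentence is meant to override the opening SAE rule. The last row then stops being a conflict, because unrelated SAEs are simply left out by design. The second row remains. That event is a UPIRTSO by the protocol's own definition, and the closing sentence names UPIRTSOs explicitly among the events it restricts.

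**Step 4: does 6.5 point the same way?** Section 6.5 asks for immediate reporting of a possibly related SAE that arises after the study period. Under the closing sentence of 6.6.1, the same event during the study need not go to the IRB. Because 6.5 names no recipient, this shows inconsistent thresholds rather than two conflicting instructions about the IRB.

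**Step 5: what happens after the change?** With 'at least possibly related' in both places, the first three rows become 'report' under the opening SAE rule and the closing sentence alike. For UPIRTSOs the restriction no longer removes anything, since possible relatedness is already part of the definition. Unrelated SAEs are consistently outside individual reporting under these two rules.

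**The case against.** The strongest reply is that the closing sentence begins by confining itself to this protocol. It can be read as a specific rule that limits the general ones before it, and the UPIRTSO sentence is itself subject to IRB policy. On that reading there is one workable rule with a badly chosen word. This has force: a reader might infer that the section cannot be followed at all, and the documents do not go that far. What stands is the mismatch between 'directly' and 'possibly', which the narrowing reading does not remove.

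Other safeguards also reduce the consequence. Section 6.6.2 stops therapy at once for an SAE reasonably related to the device, without using the 'directly' bar. Section 6.5 has every adverse event recorded and followed. The IRB would probably see the events at a 5-patient halt, because its re-review is required and a form exists for each SAE. A reader might infer that the IRB could stay unaware throughout. The documents support only a gap in event-by-event notice before any halt.

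A reader might also infer that every SAE must go to the IRB whatever its cause. Section 6 describes an adverse event as "an untoward or undesirable experience associated with the use of a medical product", and section 6.4 says "Any AE related to the study intervention that results in hospitalization or surgery should be documented and reported as a serious AE". Both partly support a related-only reading, so all-cause reporting is a policy choice.

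It is tempting to put a probability on the gap. With 90 device users (Groups 1 to 3, 30 each), an assumed 6-month SAE risk p and an assumed share f of SAEs that are possibly but not directly related, the chance of at least one such event is 1 − (1 − pf)^90. This gives 9% at p = 1%, f = 10% (pf = 0.001) and 68% at p = 5%, f = 25% (pf = 0.0125). Neither input is in the documents, and the spread shows that the answer only reflects the assumptions.

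Finally, section 8.2 discloses that the device's inventor was reviewed and cleared to act as primary investigator. A reader might infer that the narrower wording was meant to limit reporting. Nothing in the documents supports that.

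**Conclusion.** The point holds as a defect in the reporting rule. The closing sentence of 6.6.1 uses an undefined bar that excludes serious events meeting the protocol's own UPIRTSO definition, and no other text in the documents repairs this. Followed as written, it allows a possibly related serious event during the study to go unreported to the IRB before any halt, on the sponsor-investigator's judgement.

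The conclusion rests on the plain meaning of 'directly' against 'possibly'. Confidence in the textual mismatch is high. Confidence that reports would actually be missed is lower, because the IRB policy cited in 6.6.1 cannot be seen and may require some of them. The number of affected events cannot be stated without an SAE rate. This is a safety-oversight matter that should be corrected. The basis of the 5-patient count in 6.6.2 is a separate clarification and not part of this point.

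**What to change.** In the closing sentence of 6.6.1, replace 'directly related' with 'at least possibly related'. In the opening of 6.6.1, keep the requirement for a form on every SAE, and apply the same words, 'at least possibly related', to the rule that sends the form to the IRB. The two ends of the section then agree with each other, with the section 6 definition and with the wording of 6.5.

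The cost is two edited sentences in a protocol amendment. Compared with the closing sentence read strictly, there would probably be a small number of extra IRB submissions, though the documents give no basis for a count. The forms are already completed and entered in the research database, so the added work is sending them. Compared with the opening sentence read alone, the change leaves unrelated SAEs out of individual reporting. If the sponsor and the IRB prefer to receive every SAE, they can delete the closing sentence instead. Sample size, visits and analyses are unchanged.

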### **6.6.2 Stopping Rules**

Any serious adverse event which is determined to reasonably be related to the study device by the sponsor-investigator will result in immediate discontinuation of the therapy. If 5 patients develop serious adverse events, the study will be halted with re-review required by the Mayo IRB prior to consideration of study resumption.

### **6.6.3 Medical Monitoring**

Medical monitoring of serious adverse events will be performed by the study investigator on a monthly-basis if serious adverse events have been reported.

## **7 Data Handling and Record Keeping**

### **7.1 Confidentiality**

Information about study subjects will be kept confidential and managed according to the requirements of the Health Insurance Portability and Accountability Act of 1996 (HIPAA). Those regulations require a signed subject authorization informing the subject of the following:

- What protected health information (PHI) will be collected from subjects in this study
- Who will have access to that information and why
- Who will use or disclose that information
- The rights of a research subject to revoke their authorization for use of their PHI.

In the event that a subject revokes authorization to collect or use PHI, the investigator, by regulation, retains the ability to use all information collected prior to the revocation of subject authorization. For subjects that have revoked authorization to collect or use PHI, attempts should be made to obtain permission to collect at least vital status (long term survival status that the subject is alive) at the end of their scheduled study period.

### **7.2 Source Documents**

Source data comprise all information, original records of clinical findings, observations, or other activities in a clinical trial necessary for the reconstruction and evaluation of the trial. Source data are contained in source documents. Examples of these original documents, and data records include: hospital records, clinical and office charts, laboratory notes, memoranda, subjects' diaries or evaluation checklists, pharmacy dispensing records, recorded data from automated instruments, copies or transcriptions certified after verification as being accurate and complete, microfiches, photographic negatives, microfilm or magnetic media, x-rays, subject files, and records kept at the pharmacy, at the laboratories, and at medico-technical departments involved in the clinical trial. When applicable, information recorded on the CRF shall match the Source Data recorded on the Source Documents.

### **7.3 Records Retention**

The sponsor-investigator will maintain records and essential documents related to the conduct of the study. These will include subject case histories and regulatory documents.

The sponsor-investigator will retain the specified records and reports during the study and for the longer of the following;

1. As outlined in the Mayo Clinic Research Policy Manual –“Retention of and Access to Research Data Policy”

OR

2. A period of 2 years after the latter of the following two dates: The date on which the investigation is terminated or completed, or the date that the records are no longer required for purposes of supporting a premarket approval application or a notice of completion of a product development protocol.

## **8 Study Finances**

### **8.1 Funding Source**

This study is a Mayo Funded study.

### **8.2 Conflict of Interest**

[name] is the inventor and developer of the RestoreX® device. His conflict has previously been reviewed with the Mayo Clinic Conflict of Interest Review Board, and following review, it has been determined that [name] is able to conduct these studies as a Primary Investigator (IRB17-001283).

### **8.3 Subject Stipends or Payments**

Subjects will not receive payment for their participants; however, they will be able to keep the study device following completion of the study.

#### **8.4 Regulatory Information**

PathRight Medical has registered the RestoreX® device with the FDA as a Class I device, similar to limb orthotics (see Attachment – RCRI Position Paper). The device is available without a prescription and may be purchased by the general public. As such, clinical studies are not required prior to its routine use, and the current studies are being done as an investigator-initiated project to determine its potential role in length of penile prosthesis inserted.

